5.1.1.9. Duration of Grade 3/4 Neutropenia

Grade 3/4 neutropenia is defined as the lab value of ANC \geq Grade 3/4 event per CTCAE toxicity grade criteria (i.e. ANC value is $< 1.0 \times 10^9/L$). For the treatment period, the total number of Grade 3/4 neutropenia events is the number of cycles where at least one ANC value is $< 1.0 \times 10^9/L$. For example, if Cycle 2 has two ANC values that are both $< 1.0 \times 10^9/L$, this only counts as one event. If a patient did not have any ANC \geq Grade 3/4 events, the value of 0 will be assigned to that patient. Unscheduled data and the actual assessment date (rather than visit date) will be included in the derivation.

Within each cycle, the duration (days) of each reported Grade 3/4 neutropenia event is defined as the number of days from the date of first ANC value of $< 1.0 \times 10^9/L$ observed between start of cycle and end of cycle, to the date of first ANC value $\geq 1.0 \times 10^9/L$ that meets the following criteria: (1) occurs after the ANC value of $< 1.0 \times 10^9/L$ and (2) no other ANC values $< 1.0 \times 10^9/L$ occur between this day and end of cycle. The following censoring rules will be applied in the calculation:

- (i) For a cycle where the Grade 3/4 neutropenia event does not resolve by end of the cycle, the duration will be assigned as above except the end date will be the end of cycle.
- (ii) For a cycle where the patient dies, withdraws consent, or is lost to follow-up during the Grade 3/4 neutropenia event, the duration will be assigned as above except the end date will be the date of the last ANC assessment prior to the end of cycle.

For the treatment period, the overall duration (days) of Grade 3/4 neutropenia events is the median value among the duration (days) of Grade 3/4 neutropenia events from all cycles. The following data handling conventions will apply:

- For those patients where all event duration values are derived from cycles with censored data, the median value for that patient will be the median censored value. It will be a considered a censored value;
- For those patients where a subset of event duration values are derived from cycles with censored data, the median value for that patient will be estimated using the KM method. It will be considered as an observed value (i.e. no censored value);
- For those patients where the median event duration cannot be derived (e.g. ≤ 2 values), the longest event duration amongst all the cycles will be used regardless of censoring, but the corresponding censoring flag will be carried over for analysis.

5.1.1.10. ANC, Platelet Count, Absolute Lymphocytes, and Hemoglobin Change over Time

For the hematologic parameters consisting of ANC, hemoglobin, platelet count, and absolute lymphocytes, the observed lab values in each windowed visit as detailed in [Section 6.1.3](#) will be appropriately identified for further analysis. For the ANC, the cycle NADIR will also be obtained.

Also, for the ANC, the observed lab value at each scheduled Day 1 of a cycle will be properly flagged for further analysis. The scheduled Day 1 of cycle will follow the scheme defined in the protocol regardless of the potential cycle delay, for example, if Cycle 2 is delayed 7 days from Cycle 1 due to ANC recovery, Day 22 from the first dose date of study drug in Cycle 1 will be the scheduled Day 1 of Cycle 2.

5.1.1.11. Time to First Major Adverse Hematologic Event (MAHE)

As a composite measure of trilaciclib effect, MAHE is based on a combination of individual components specified in [Table 5](#), which also include details about the derivation or data source for each component. Time to first occurrence of a MAHE event is defined as the first time to observe an interested event among all the component, starting from the first dose date of study drug administration.

Therefore, for a patient with presence of MAHE events, time (months) to first occurrence of a MAHE event will be the minimum among the 7 potentially derived duration (i.e. calculated as (date of first occurrence of a MAHE component event – first dose date of study drug administration + 1)/30).

Table 5 Component of MAHE and the Suggested Data Source/Derivation Algorithm

Seq #	Component of MAHE	Criteria to identify the date of first occurrence of event
1	Hospitalization for a hematologic event (e.g. febrile neutropenia, thrombocytopenia, hemoptysis, etc)	Each hospitalization for a hematologic event (e.g. febrile neutropenia, thrombocytopenia, hemoptysis, etc.) is captured in AE data of electronic database. The event terms are coded using the MedDRA Version 20.1. Some suggested PTs are listed in Table 6 . These PTs will be broken into those that are always counted if they result in hospitalization, and those that will be subject to a case by case medical review to determine if the hospitalization is a hematologic event. All review will be finalized prior to study unblinding.
2	Febrile neutropenia	Detailed in Section 5.1.1.1
3	Death related to treatment (including backbone chemotherapy and trilaciclib)	An AE with its outcome being death, if its relationship to any of the study drugs (etoposide, carboplatin, or trilaciclib) is “Possibly Related”, “Probably Related”, or “Definitely Related”.
4	Dose delay/reduction due to ANC or platelet counts	Detailed in Section 5.1.3.4
5	Duration of Grade 4 neutropenia > 5 days	Detailed in Section 5.1.1.8 . If the duration (days) within a cycle is censored, even the duration of Grade 4 neutropenia

Seq #	Component of MAHE	Criteria to identify the date of first occurrence of event
		is \leq 5 days, the event will still be considered to meet the criteria. 5.1.1.2
6	RBC transfusion (actual or eligible)	Detailed in Section 5.1.1.2
7	Platelet transfusion (actual or eligible)	Detailed in Section 5.1.1.3

A patient with absence of any MAHE events will be censored at the date of the last assessment/contact date prior to or on the day of study completion/discontinuation, or lost to follow-up, whichever is earlier.

Table 6 PT list for Meeting the Criteria of Hospitalization for a Hematologic Event

PTs always included	PTs to be reviewed for possible inclusion
FEBRILE NEUTROPENIA	RESPIRATORY FAILURE
NEUTROPENIA	PNEUMONIA
ANAEMIA	HAEMOPTYSIS
THROMBOCYTOPENIA	
NEUTROPHIL COUNT DECREASED	
HEMOGLOBIN DECREASED	
ANAEMIA MACROCYTIC	
RED BLOOD CELL COUNT DECREASED	
PLATELET COUNT DECREASED	

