### 6.1.3. Criteria for Subsequent Cycles and Study Duration

In all parts of the study, study drug administration will continue until disease progression per Response Evaluation Criteria in Solid Tumors (RECIST), Version 1.1, unacceptable toxicity, withdrawal of consent, or discontinuation by investigator (eg, after completing 6 cycles), whichever occurs first. Treatment cycles will occur consecutively without interruption, except when necessary to manage toxicities or for administrative reasons as described below.

In order to start Cycle 2 and subsequent cycles as scheduled, patients should meet all of the following criteria:

- ANC  $\geq 1.5 \times 10^9/L$
- Platelet count  $\geq 100 \times 10^9/L$

- Nonhematologic drug-related toxicities (except alopecia) must be  $\leq$  Grade 1 or have returned to baseline

A delay of up to 2 weeks is permitted to allow recovery from any toxicity in order to meet the continuation criteria for organ function. If patients meet the criteria for starting the subsequent cycle as described above, a delay of up to 1 week is permitted for administrative reasons (eg, holiday, vacation, etc.). If the subsequent cycle is delayed, the patient should still complete the clinical laboratory assessments and the FACT-L and FACT-An questionnaires on the scheduled Day 1, as well as on the actual first dosing day of the next cycle. A patient will be discontinued from the study if recovery from any toxicity, in order to meet the continuation criteria for organ function, and any delay for administrative reasons requires a total delay of  $> 2$  weeks (see Section 8.4.4.2.1 and Table 8-2).

After discontinuation of study drug, patients should be strongly encouraged to complete all scheduled assessments through the end of their current 21-day treatment cycle, including the patient-reported outcome (PRO) scales; CBC assessment on Day 22; the Post-Treatment Visit; and the Survival Follow-up Phase of the study.

The G1T28-02 study will be completed when the Survival Follow-up Phase has been completed, or upon sponsor termination of the study.

The total study duration is at least 29 months.

Part 1 is expected to be approximately 18 months, assuming 12 months of accrual, 2 weeks for screening, 4.5 months of treatment (assuming 6 cycles), and 1 month of safety follow-up.

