Part 2 will begin after the Part 2 dose is identified from the Phase 1b dose-finding portion of Part 1 and the Phase 2a expansion portion of Part 1 has completed enrollment, which is expected to occur approximately 12 months after Part 1 begins. Part 2 is expected to be approximately 17 months, assuming 11 months of accrual, 2 weeks of screening, 4.5 months of treatment (assuming 6 cycles), and 1 month of safety follow-up.

The Survival Follow-up Phase of the study will continue until at least 50% of the randomized patients in Part 2 have died.

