#### 6.1.4. Safety Assessments

Safety assessments will include monitoring of AEs, vital signs measurements, physical examinations, ECGs, and clinical laboratory studies as described in Section 11.3. Safety surveillance reporting of AEs commences at the time that informed consent is obtained and continues through the Post-Treatment Visit.

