### **8.6. Prior and Concomitant Medications and Procedures**

All concomitant medications including prescription medications, over-the-counter preparations, growth factors, blood products, and parenteral nutrition taken during the 14 days before the date of enrollment, during the study treatment, and through 30 days after the last dose of study drug will be documented. Documentation will include information regarding start and stop dates, dose(s), and reasons for the medication use.

Administration of other concomitant nonprotocol anticancer therapies prior to progression is not permitted while on this study.

Administration of other concomitant investigational agents for any indication is not permitted while on this study.

Concomitant radiation therapy treatment for SCLC will be regarded as disease progression, and is not permitted while on this study.

Caution should be exercised when administering etoposide phosphate with drugs that are known to inhibit phosphatase activities (eg, levamisole hydrochloride). Although carboplatin has limited nephrotoxic potential, caution should be exercised when administering carboplatin with aminoglycosides, which has resulted in increased renal and/or audiologic toxicity. Any medication that is contraindicated when using etoposide or carboplatin is not permitted, and special warnings and precautions for use of carboplatin and etoposide should be observed.

Necessary supportive care such as antiemetics, antidiarrheals, etc., per the standard of care at the study center will be permitted. **Administration of hematopoietic growth factors in Cycle 1 will not be permitted (ie, no growth factors should be used prior to the actual Cycle 2 Day 1 dosing visit).** However, hematopoietic growth factors may be utilized in subsequent cycles at the investigator's discretion as stated in Section 8.4.4.2. To reduce potential immune system interactions, the use of dexamethasone as an antiemetic should be minimized where possible.

G1T28 is a time-dependent inhibitor of CYP3A4 and is a substrate for CYP3A4. G1T28 exposure may be altered by concomitant use of drugs that are strong CYP3A inhibitors or inducers. The exposure of drugs that are CYP3A substrates may be altered by concomitant use of G1T28 (Section 4.3.2).

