#### **10.7. Survival Follow-up Phase**

Monthly phone calls will be made to each patient that is in the long-term Survival Follow-up Phase. Patients will be followed for survival at a minimum until 50% of the patients randomized to Part 2 of the study have died. In addition, for patients who have not had disease progression at the time of study drug discontinuation, tumor assessments, including all sites of disease, will be assessed radiologically by CT or MRI, as performed at screening,

every 2 months (approximately  $60 \pm 7$  days) until the occurrence of progressive disease or study completion.

The following information will be collected monthly for all patients:

- Survival status
- Details of any anticancer treatment

The following additional information will be collected at  $60 \pm 7$  days after the Post-Treatment Visit (**Part 2 only**):

- Immunologic markers blood sample collection
- Hematology sample collection

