#### 11.3.1.6. Method, Frequency, and Time Period for Detecting Adverse Events and Serious Adverse Events

Safety surveillance reporting of AEs commences at the time of informed consent and continues through 30 days after last dose of study drug (eg, the Post-Treatment Visit).

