6.2. Analysis Methods

6.2.1. Patient Disposition

A summary table will be generated to provide the following by study part, as appropriate:

- Number of patients screened
- Number and percentage of screening failures
- Reason for screening failure
- Number of patients dosed (Part 1 only)
- Number of patients randomized (Part 2 only)
- Number of patients randomized and not dosed (Part 2 only)
- Number of patients dosed and not randomized (Part 2 only)

A separate table will be presented to show the patients included in each analysis set and reason for exclusion from an analysis set.

Patient status at treatment and study completion will be listed and summarized. The listing will include whether patients discontinued from the treatment and the reasons for the discontinuation, along with the date of first and last dose and the date of completion or discontinuation from the treatment. The same information will be provided for patients who discontinued from the study. The following summaries will be added to the disposition table:

- End of treatment status (discontinued study drug or continue on study drug)
- Number and percentage of patients in the FAS who discontinued study drug
- Number and percentage of patients in the FAS who discontinued study drug before 6 cycles
- Number and percentage of patients in the FAS who discontinued study drug after 6 cycles
- Reason for study drug discontinuation
- End of study status (discontinued study or continue in the survival follow-up)
- Number and percentage of patients in the FAS who discontinued the study
- Reason for study discontinuation
- Death and reason for death

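### Patients without a MAHE are censored in survival follow-up, after most MAHE components have stopped being ascertained, so the hazard ratio can be distorted in either direction when the arms differ in treatment length

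*SAP*

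**What the plan says.** **Censoring date.** SAP 5.1.1.11 has MAHE-free patients "censored at the date of the last assessment/contact date prior to or on the day of study completion/discontinuation", or at loss to follow-up, whichever comes first. Protocol 6.1.3 fixes when completion happens: "The G1T28-02 study will be completed when the Survival Follow-up Phase has been completed, or upon sponsor termination of the study". The same section adds: "The Survival Follow-up Phase of the study will continue until at least 50% of the randomized patients in Part 2 have died". Contact goes on throughout; Protocol 10.7 states: "Monthly phone calls will be made to each patient that is in the long-term Survival Follow-up Phase". The disposition table in SAP 6.2.1 sets discontinuing the study against continuing in survival follow-up, so a patient in follow-up has not discontinued the study.

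**Ascertainment.** Protocol 6.1.4: "Safety surveillance reporting of AEs commences at the time that informed consent is obtained and continues through the Post-Treatment Visit". Protocol 11.3.1.6 puts that limit at 30 days after the last dose. Protocol 8.6 applies the same limit to concomitant medications, blood products included: what is taken "through 30 days after the last dose of study drug will be documented". SAP Section 5 ends the last cycle at Day 36. Febrile neutropenia, Grade 4 neutropenia duration and both transfusion components are derived between start and end of a cycle (SAP 5.1.1.1 to 5.1.1.3 and 5.1.1.8). Dose delay or reduction needs ongoing treatment (SAP 5.1.3.4).

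**Analysis.** SAP 6.2.7.1 gives time to first MAHE a stratified p-value, a Cox hazard ratio with 80% CI, and a cumulative incidence display. Tests are two-sided at 20%. No sensitivity analysis of the censoring rule is given.

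**The concern.** A Cox model compares each patient who has an event with everyone still counted as at risk on that day. Under this rule a patient who stopped chemotherapy without a MAHE stays in that comparison although almost none of the seven components can now be recorded. The arm that stops earlier collects more of these patients, so its apparent hazard falls. MAHE is the composite of the 17 prospectively defined analyses in SAP Table 3 and carries a p-value. The eight binary endpoints beside it are confined to the treatment period; MAHE is not.

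**Working it through.** **1. The plan's own figures.** The only design figures are the precision statements in Protocol 13.1 and SAP 2.3, for 35 patients per arm. The Wilson half-width at p = 0.5 is 1.96 × √(0.25/35 + 1.96²/(4 × 35²)) / (1 + 1.96²/35) = 0.157. The t-based half-width is 2.032/√35 = 0.344 SD. Both reproduce. Neither bears on MAHE, for which no rate, hazard ratio or event count is stated.

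**2. Where ascertainment ends.** A last dose on Day 3 plus 30 days plus the 3-day visit window is Day 36. The end of the last cycle and the latest Post-Treatment Visit therefore coincide.

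**3. The mechanism by hand.** Assume 35 patients per arm, a 15% MAHE risk per cycle in both arms (true ratio 1.0), 4 cycles on placebo and 6 on trilaciclib, and no deaths.
- MAHE-free after 4 cycles, each arm: 35 × 0.85⁴ = 18.27. Events so far, each arm: 35 − 18.27 = 16.73.
- Cycle 5, trilaciclib only: 0.15 × 18.27 = 2.74 events. Cycle 6: 18.27 − 2.74 = 15.53 at risk, and 0.15 × 15.53 = 2.33 events.
- Under the SAP rule the 18.27 placebo patients remain in the risk set. Expected trilaciclib events are 16.73 + 2.74 × 18.27/36.54 + 2.33 × 15.53/33.80 = 16.73 + 1.37 + 1.07 = 19.17. Observed are 16.73 + 2.74 + 2.33 = 21.80.
- Placebo: observed 16.73, expected (21.80 + 16.73) − 19.17 = 19.36.
- Ratio: (21.80/19.17)/(16.73/19.36) = 1.137/0.864 = 1.32.
- With follow-up ended at the window, no placebo patient is at risk in cycles 5 and 6. Those events add nothing and the ratio is 1.00.

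Simulating 4 v 6 cycles with deaths included, and observation to Day 36 of the last cycle, gives 1.27 or 1.17 for a placebo MAHE risk of 50% or 80% over six cycles.

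**4. Range over assumptions** (simulated, true ratio 1.0, at most 6 cycles, median survival about 10 months):

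| Stopping per cycle, placebo v trilaciclib | MAHE timing | SAP rule | Window censoring |
|---|---|---|---|
| 10% v 5% | constant, 15% per cycle | 1.09 | 1.00 |
| 15% v 5% | constant, 15% per cycle | 1.19 | 1.00 |
| 25% v 7% | constant, 15% per cycle | 1.33 | 1.00 |
| 5% v 15% | constant, 15% per cycle | 0.84 | 1.00 |
| first three pairs | front-loaded (50/15/5% or 40/20/10/5%) | 1.02–1.07 | about 1.00 |
| 25% v 5% | all in cycle 1 | 1.00 | 1.00 |

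**5. Effect on the test and on a real benefit** (35 per arm, constant hazard, placebo MAHE risk 50% or 80% over six cycles). With no true effect, unequal treatment length raised rejection at the 20% level to 0.25–0.39; window censoring gave 0.185–0.210. With a true ratio of 0.6 and mean cycles of 4.15 on placebo v 5.30 on trilaciclib, the SAP rule gave 0.74 or 0.73, and rejection fell from 0.48 to 0.32 or from 0.62 to 0.40. With the cycle counts reversed it gave 0.50 or 0.52, and rejection rose from 0.46 to 0.63 or from 0.63 to 0.78. Equal treatment length left only slight attenuation, to 0.605–0.620.

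**The case against.** Several stronger readings are tempting, and the documents do not support them.

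- *The ratio is biased whenever treatment length differs.* It is not. Follow-up after the last MAHE adds nothing to the partial likelihood, so a phone call many months later does no harm in itself. Events must occur after some patients have stopped.
- *The bias runs against trilaciclib.* SAP Section 4 hypothesises fewer delays and fewer hematologic events over multiple cycles. It does not say that trilaciclib patients will receive more cycles, and the reverse pattern favours the drug.
- *No MAHE can be recorded after the window.* Protocol 11.3.1.9 requires late drug-related serious events to be reported, so treatment-related deaths and related hospitalizations can still enter. Part 2 also has one hematology sample about 60 days after the Post-Treatment Visit, but it lies outside any cycle.

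Two further arguments have weight. First, the SAP names no estimand. If the target is the proportion who ever have a MAHE, including time off chemotherapy, a flat curve after treatment is what the definition implies. That would suit the cumulative incidence display, but it does not justify counting largely unascertained time as event-free in a tested hazard ratio. Second, the wording may be loose: SAP 6.2.5 uses study completion or discontinuation for concomitant medications, which are documented only to 30 days. Yet the MAHE rule also names contact, and a programmer following it would reach the phone calls.

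The study's primary objective is safety, and Protocol 13.2.3 calls it descriptive, which limits the severity. SAP 6.2.7.1 nevertheless reports a p-value.

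**Conclusion.** The concern holds in a conditional form. Read with the protocol's definition of completion, the censoring date runs past the period in which most MAHE components are ascertained. The hazard ratio and p-value are distorted if the arms differ in treatment length and MAHEs occur after some patients have left that period. For a true ratio of 1.0 the distortion is small with front-loaded events (1.02–1.07), larger with a constant hazard and earlier stopping on placebo (about 1.1–1.35), reversed if trilaciclib stops earlier (about 0.84), and absent if every event precedes the first discontinuation. All of these rest on assumed event and stopping rates. They measure distortion against the hazard while MAHE is ascertained. This should be fixed; it does not invalidate the other prospectively defined analyses.

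**What to change.** Before unblinding, amend SAP 5.1.1.11 so that, in the primary MAHE analysis:
- a patient without a MAHE is censored at the earlier of Day 36 of the last cycle and the last assessment;
- component events count only within that window, for all seven components;
- the handling of deaths unrelated to treatment is stated, for the Cox model and for the cumulative incidence display.

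Report the present rule, with late treatment-related deaths and hospitalizations counted, as a sensitivity analysis.

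The cost is a short text change and one extra run, with no new data. There are two downsides. Events after Day 36 leave the primary analysis. Some informative censoring may also remain if toxicity drives stopping: when one assumed frailty governed both stopping and MAHE, the ratio after the change was still about 1.02–1.09 for a true 1.0. That is closer than under the present rule, but not exact. A choice between the two rules made after unblinding would depend on the data.

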5.1.2. Exploratory Efficacy Endpoints

5.1.2.1 Grade 2 or Greater Nephrotoxicity

For any post-baseline creatinine assessment, an event of grade \geq 2 nephrotoxicity is defined as the observed value $>1.5 \times$ baseline value, or $> 1.5 \times$ Upper Limit of Normal Range (ULN).

Within a cycle, for each nephrotoxicity event, the occurrence of a creatinine value meeting the criteria outlined above is described using a binary variable (Yes or No); Yes, if the designated event is observed, No for other scenarios. For the treatment period, the total number of nephrotoxicity events where the creatinine value meets the criteria is the number of cycles where at least one lab value meets the criteria. For example, if Cycle 2 has two values that both meet criteria, this only counts as one event. If a patient does not have any lab values meeting the criteria, the value of 0 will be assigned to that patient. Unscheduled data and the actual assessment date (rather than visit date) will be used for these analyses.

Any occurrence of a Grade \geq 2 nephrotoxicity during the treatment period is defined as a binary variable (Yes or No); Yes if total number of Grade \geq 2 nephrotoxicity events \geq 1 is observed, No for other scenarios.

